**10.1.2.7. Lot-to-lot consistency: MenABCWY - ACWY component**

One thousand two hundred thirty-three (1,233) evaluable subjects (411 evaluable subjects in each in ABCWY-1, ABCWY-2 and ABCWY-3 groups) are needed to demonstrate, for all pairs of lots, the two-sided 97.5% CIs for the ratio of hSBA GMTs of antibodies against serogroups A, C, W and Y are within the [0.5; 2.0] equivalence interval.

Assuming standard deviations as the 80% upper confidence limit of the ones observed in a previous GSK study with MenABCWY vaccine (V102\_15) to account for possible more variation in new data, an assumed underlying ratio between lots of 1.2 and independency, a single equivalence test based on 411 evaluable subjects per lot group has power 99.0%→99.9% (see [Table 20](#)). The resulting overall power is 96.1%, because the total number of comparisons is 12 (three pairwise comparisons for the 4 serogroups A, C, W, and Y).

**Table 20 Power calculation to demonstrate lot-to-lot consistency**

Serogroup	SD	80% CI (UL)	Assumed underlying ratio	N	Power
A	0.5651582	0.616702951	1.2	411	99.7%
C	0.5048067	0.550847146	1.2	411	>99.9%
W	0.370505	0.404296579	1.2	411	> 99.9%
Y	0.627423	0.684646557	1.2	411	99.0%
Total (12 pairwise comparisons)					96.1%%

Note: SD – standard deviation; CI – confidence interval; UL – upper limit; N – number of evaluable subjects in each MenABCWY vaccine lot;

**10.1.2.8. Immunological non-inferiority: MenABCWY vs. MenACWY in subjects without a previous MenACWY vaccination (unprimed)**

Assuming at least 70% subjects without a previous MenACWY vaccination (unprimed), there will be at least 863 (70% out of 1233) evaluable subjects in the ABCWY group (pooled lots), at 1 month after the last vaccination, and 96 (70% out of 137) in the ACWY group at 1 month after the MenACWY vaccination (at Month 7 for ABCWY group (pooled lots) and at Month 1 for ACWY group). This sample size is sufficient to demonstrate that the lower limit of the two-sided 97.5% CIs for by percentage of subjects with 4-fold rise in hSBA titres against MenACWY indicator strains A, C, W and Y is > -10%.

Assuming similar underlying immune response after 2 doses of MenABCWY vaccine, as previously observed in study V102\_16 (Column 2 and 3 of [Table 21](#)), the resulting overall power is 99.6%.

**CONFIDENTIAL**205416 [MENB REC 2ND GEN-038 (V72\_72)]  
Protocol Amendment 4 Final**Table 21 Power calculation to demonstrate non-inferiority for serogroups A, C, W and Y of MenABCWY compared to MenACWY in subjects without a previous MenACWY vaccination (unprimed), at 1 month after the second dose vs 1 month after a single dose**

Serogroup	MenABCWY % 4-fold rise (2 doses)	MenACWY % 4-fold rise (1 dose)	Power (%) for 70% unprimed subjects
A	92.4%	59.1%	>99.9%
C	95.4%	56.9%	>99.9%
W	80.4%	34.0%	>99.9%
Y	90.9%	62.8%	>99.9%
Total			99.6%

Unprimed = Subjects without a previous MenACWY vaccination

**10.1.2.9. Vaccine effectiveness (Test-based): MenABCWY**

As the underlying assumptions for MenABCWY 0-6M is the same as MenB, see Section [10.1.2.1](#).

**10.1.2.10. Effectiveness non-inferiority: MenABCWY vs. rMenB+OMV NZ**

The target number of evaluable subjects of 684 (in ABCWY group (pooled lots)) and 684 (in the Control group) at 1 month after the last vaccination is sufficient to demonstrate that the lower limit of the two-sided 97.5% CI for the difference in percentages of samples with bactericidal activity at 1:4 dilution in the ABCWY group (pooled lots) and in the Control group is above -5%.

Assuming the percentage of samples with bactericidal serum activity at 1:4 dilution in ABCWY group (pooled lots) 75% and 75%-78% in MenB, the power to show non-inferiority is  $\geq 99.8\%$ . ([Table 22](#)).

**Table 22 Power calculation to demonstrate NI of MenABCWY to MenB**

Percentages of killed samples MenABCWY 0-6M	Percentages of killed samples MenB	Expected Difference	N per group	Power
75%	75%	0%	684	> 99.9%
75%	76%	-1%	684	> 99.9%
75%	77%	-2%	684	> 99.9%
75%	78%	-3%	684	99.8%
75%	79%	-4%	684	64%

**10.1.2.11. Effectiveness (Responder-based): MenABCWY**

As the underlying assumptions for MenABCWY 0-6M is the same as MenB, see Section [10.1.2.2](#).

**CONFIDENTIAL**205416 [MENB REC 2ND GEN-038 (V72\_72)]  
Protocol Amendment 4 Final**10.1.2.12. Non inferiority of MenABCWY vs rMenB+OMV NZ measured by percentage of subjects with 4-fold rise in hSBA titres against MenB component indicator strains post 2nd dose****(Amended 9 May 2021)**

Key secondary objective is to demonstrate non inferiority of MenABCWY vs rMenB+OMV NZ measured by the percentages of subjects with 4-fold rise in hSBA titres against the *N. meningitidis* serogroup B indicator strains post 2nd dose. Six hundred twenty (620) subjects are needed to demonstrate the immunological non-inferiority of the MenABCWY vaccine compared to the rMenB+OMV NZ as measured by the percentages of subjects achieving a 4-fold rise in hSBA titres against *N. meningitidis* serogroup B indicator strains at 1 month after the last MenABCWY vaccination (0,6-months schedule) and 1 month after the MenB vaccination (0,2,6-months or 0,6-months or 0,2-months) with 81% power calculated for three strains (96217 (NadA), M14459 (fHbp), and **M13520** (NHBA)). NZ98/254 (PorA) is not powered for as the 4-fold rate for MenABCWY is predicted to be at least 10% less than the 4-fold rate for MenB.

Non-inferiority will be demonstrated if the LL of the 2-sided 97.5% CI for the group difference in percentage of subjects achieving a 4-fold rise in hSBA titres against all *N. meningitidis* serogroup B indicator strains is above -10%. [Table 23](#) presents the power to meet the objective.

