**10. STATISTICAL CONSIDERATIONS****10.1. Sample size determination**

(Amended 9 May 2021)

Three thousand six hundred fifty-one (3,651) subjects are to be enrolled in the study.

[Figure 1](#) presents the study design overview with the breakdown of sample size per study arm:

- MenB\_0\_2\_6: 912 subjects
- MenB\_0\_6: 912 subjects
- ABCWY-1: 548 subjects
- ABCWY-2: 548 subjects
- ABCWY-3: 548 subjects
- ACWY: 183 subjects.

It is assumed that 25% of the subjects will drop-out and not contribute to an evaluable result. The remaining subjects who do give an evaluable result provide 90% power to reject all hypotheses for the primary objectives of rMenB+OMV NZ and 92% power to reject all hypotheses for the primary objectives of MenABCWY vaccine. Additionally, the study is powered to reject key secondary objective for three *N. meningitidis* serogroup

**CONFIDENTIAL**205416 [MENB REC 2ND GEN-038 (V72\_72)]  
Protocol Amendment 4 Final

B indicator strains (96217 (NadA), M14459 (fHbp), and *MI3520* (NHBA)) with 81% power.

[figure not shown]
An explanation of the testing strategy and hypotheses can be found in Section 10.1.1 and its sub-sections. A breakdown of the power for the individual objectives can be found in Section 10.1.2 and its sub-sections.

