**10.3.3.11. Effectiveness (Responder-based): MenABCWY**

See Section [10.3.3.2](#)

**10.3.4. Secondary effectiveness and immunogenicity analyses****10.3.4.1. Immunological non-inferiority: MenABCWY vs. rMenB+OMV NZ**

(Amended 9 May 2021)

Analysis set: PPS will be the primary analysis population.

Statistical method: The percentages of subjects with 4-fold rise in hSBA titres against *N. meningitidis* serogroup B indicator strains (M14459, 96217, **M13520** and NZ98/254 for fHbp, NadA, NHBA and PorA P1.4 antigens, respectively) at 1 month after the last vaccination for the ABCWY group (pooled lots) (Day 211, Month 7) and 1 month after the 3-dose vaccination series (Day 211, Month 7) in MenB\_0\_2\_6 group or 2-dose vaccination series (Day 211, Month 7) in MenB\_0\_6 group or 2-dose vaccination series (Day 91, Month 3) in MenB\_0\_2\_6 group and the corresponding exact 2-sided 95% CIs based on Clopper-Pearson method will be calculated [Clopper, 1934]. The 95% CIs for the difference in percentages between ABCWY group (pooled lots) and MenB\_0\_2\_6 group and MenB\_0\_6 group will be constructed using the method of Miettinen and Nurminen [Miettinen, 1985].

Non-inferiority criterion: Non-inferiority of MenABCWY vaccine for the proportion of subjects with 4-fold rise will be demonstrated if the lower limit of the 2-sided 95% CI for the difference in percentage of subjects with 4-fold rise between the 2 groups (ABCWY group (pooled lots) – selected MenB group) is above -10%.

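### Section 10.1.2.12 requires non-inferiority on all four MenB indicator strains but powers only three; with PorA planned at 53% vs 76%, that rule has about 0% power

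*Protocol*

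**What the plan says.** The objective is non-inferiority of MenABCWY to rMenB+OMV NZ in the percentage of subjects with a 4-fold rise in hSBA titre against the MenB indicator strains. Four strains are defined. Section 10.3.4.1 lists M14459, 96217, M13520 "and NZ98/254 for fHbp, NadA, NHBA and PorA P1.4 antigens, respectively".

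- **Success rule in 10.1.2.12.** "Non-inferiority will be demonstrated if the LL of the 2-sided 97.5% CI for the group difference in percentage of subjects achieving a 4-fold rise" satisfies the margin for every strain; the sentence ends "hSBA titres against all *N. meningitidis* serogroup B indicator strains is above -10" (per cent).
- **Power in 10.1.2.12 and Table 23.** With 620 subjects, 81% power is given for NadA, fHbp and NHBA. For the fourth strain: "NZ98/254 (PorA) is not powered for as the 4-fold rate for MenABCWY is predicted to be at least 10% less than the 4-fold rate" (the comparator's). Table 23 enters PorA at 53% vs 76% with 0% power.
- **Power in 10.1.** "Additionally, the study is powered to reject key secondary objective for three" named strains, again with 81%.
- **Rule in Synopsis Table 1, Table 6 and 10.3.4.1.** The margin is the same, but the interval is 95%. In 10.3.4.1, non-inferiority "will be demonstrated if the lower limit of the 2-sided 95% CI for the difference in percentage of subjects with 4-fold rise" exceeds -10%. None of the three places says whether one verdict covers all strains or each strain has its own.

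**The concern.** The rule and the power figure in 10.1.2.12 describe different hypotheses. The rule covers every indicator strain, while the power covers three of the four. The strain left out of the power is the one that the protocol itself expects to miss the margin.

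Elsewhere the protocol keeps rule and power together. Non-inferiority to MenACWY must hold for each serogroup (10.1.1.8), and Table 21 gives a total over all four. Lot consistency must hold for every pair of lots and every serogroup, and Table 20 gives power over all 12 comparisons.

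This is called a key secondary objective and is framed as a demonstration with a numerical criterion, so the wording decides what the trial may conclude. If PorA behaves as planned and the other three strains succeed, 10.1.2.12 says the objective failed. The other sections could be read as allowing a conclusion for the three strains. That choice should not be open once the PorA result is known.

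**Working it through.** **Inputs.** From 10.1.2.12: margin 10 percentage points, 97.5% two-sided interval (z = 2.2414), 620 subjects. From Table 23: the planned rates. The protocol does not say whether 620 is per group or in total. Read as per group, it reproduces Table 23. Read as a total (310 per group), it gives 80.8%, 61.8% and 60.3%, which does not match.

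**Formula.** Power = Φ((p1 − p2 + 0.10)/SE − z), with SE = √[p1(1 − p1)/n + p2(1 − p2)/n].

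**Step 1: reproduce Table 23 at n = 620 per group.**

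| Strain | p1 vs p2 | SE | (p1 − p2 + 0.10)/SE | minus 2.2414 | Power | Table 23 |
|---|---|---|---|---|---|---|
| NadA | 80% vs 80% | 0.0227 | 4.40 | 2.16 | 98.46% | 98.5% |
| fHbp | 60% vs 60% | 0.0278 | 3.59 | 1.35 | 91.19% | 91.2% |
| NHBA | 45% vs 45% | 0.0283 | 3.54 | 1.30 | 90.28% | 90.3% |
| PorA | 53% vs 76% | 0.0264 | −4.93 | −7.17 | 3.8 × 10⁻¹³ | 0% |

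**Step 2: three-strain power.** 0.9846 × 0.9119 × 0.9028 = 0.811. This is the stated 81%. The product treats the strains as independent.

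**Step 3: power of the rule as worded in 10.1.2.12.** Multiplying by PorA gives about 3.1 × 10⁻¹³. Independence does not matter here, because a joint success cannot be more likely than success on PorA alone. In 200,000 simulated trials none met the four-strain rule.

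**Step 4: sensitivity.**

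- With a 95% interval, PorA power is 2.8 × 10⁻¹² and joint power 2.5 × 10⁻¹².
- With 684 per group at 97.5%, joint power is about 5 × 10⁻¹⁴.
- Section 10.1.2.12 predicts in words a PorA deficit of at least 10%, read here as percentage points. At a deficit of exactly 10 points the true difference sits on the margin, so PorA power equals the one-sided error rate: 1.25% (97.5% interval) or 2.5% (95% interval). Joint power cannot exceed that.

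**Step 5: interval level.** With z = 1.96, as the 95% interval in the objectives and analysis sections implies, the three powers become 99.27%, 94.89% and 94.28%. Their product is 88.8%. So the 81% does not match the interval stated in Synopsis Table 1, Table 6 and 10.3.4.1.

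**The case against.** A reader might infer that the protocol claims 81% power for a four-strain rule, or conceals the PorA problem. The documents do not support that. Sections 10.1 and 10.1.2.12 both limit the 81% to three named strains, 10.1.2.12 says that PorA is not powered and why, and Table 23 prints the 0%. No power figure is wrong for its stated scope.

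A reader might also infer that the objective is certain to fail. That goes too far as well. The word *all* appears only in the sample-size justification. Synopsis Table 1, Table 6 and 10.3.4.1 omit it, the 4-fold rise is defined per indicator strain, and where the protocol wants joint success elsewhere it says so plainly. A strain-by-strain reading of those sections is open. Failure also depends on the planned PorA rates, and the comparator schedule is chosen by the trial's own results.

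Finally, the objective is secondary. The text of 10.1.1 makes no primary conclusion depend on it, and Figure 2 is not reproduced in the copy reviewed, so its place in the hierarchy cannot be checked there. The three-strain scope is written down before the data, so a later three-strain conclusion would not come from nowhere.

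All of this stands, and it limits the point to a mismatch between rule and powering. It does not remove the mismatch. The only place that says how strains combine says all of them, and no section restricts success to three. The SAP was not available for this review and may state a rule, but that would not remove the contradiction within the protocol.

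**Conclusion.** The point holds as an inconsistency within the protocol. The rule worded in 10.1.2.12 has about 0% power on the plan's own PorA rates, at either interval level and with 620 or 684 per group. The 81% is correct for NadA, fHbp and NHBA at a 97.5% interval with 620 per group. Whether success is joint or per strain is left open in Synopsis Table 1, Table 6 and 10.3.4.1, and those places use a 95% interval where the power calculation uses 97.5%.

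The three-strain figures assume 620 evaluable subjects per group and independence between strains. The near-zero joint power needs only the planned PorA rates. It stays at or below 1.25% (97.5% interval) or 2.5% (95% interval) for any PorA deficit of 10 points or more.

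**What to change.** Before unblinding, put one identical rule in Synopsis Table 1, Table 6, 10.1.2.12 and 10.3.4.1. Any of three would be coherent:

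- **(a)** Success requires a lower limit above -10% for each of NadA, fHbp and NHBA. PorA is reported with its interval and pre-declared as outside the claim.
- **(b)** Non-inferiority is concluded strain by strain for all four, with the per-strain powers of Table 23 and no joint figure presented as the power of the objective.
- **(c)** *All* is kept, and the joint power is stated as about 0%.

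In the same edit, choose one interval level and quote the three-strain power that goes with it: 81% at 97.5%, or about 89% at 95%, with 620 stated as per group.

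No extra subjects, samples or assays are needed. The edit is short, but (a) is a real choice and not only wording: it takes out of the claim the strain that 12.2.2 ties to the immunodominant antigen of the OMV component, and the protocol should say so openly. Option (b) should say whether the four conclusions are adjusted for multiplicity.

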**Table 23 Power of Non inferiority of MenABCWY vs rMenB+OMV NZ**

Strain	4-fold rise (MenABCWY)	4-fold rise (rMenB+OMV NZ)	Power
96217 (NadA)	80%	80%	98.5%
M14459 (fHbp)	60%	60%	91.2%
M13520 (NHBA)	45%	45%	90.3%
NZ98/254 (PorA)	53%	76%	0%

**10.2. Populations for analyses**

For purposes of analysis, the following analysis sets are defined:

Analysis Set	Description
Enrolled Set	Subject/ Subject for whom parent(s)/LAR's agreed to participate in a clinical study after completion of the informed consent process, who meet screening/eligibility criteria and randomized and/or received study intervention or undergone an invasive procedure. Refer to Glossary of terms for definition of an enrolled subject.
Exposed Set	All subjects who received at least 1 dose of the study treatment. The allocation in a group is done in function of all administered treatments.
Full Analysis Set	All subjects who received at least 1 dose of the study treatment and have post-vaccination effectiveness or immunogenicity data
Per Protocol Set	All subjects who received at least 1 dose of the study treatment to which they are randomised and have post-vaccination data (Full Analysis Set) minus subjects with protocol deviations that lead to exclusion from the Per Protocol Set.
Solicited Safety Set	All subjects who received at least 1 dose of the study treatment (Exposed Set) who have solicited safety data
Unsolicited Safety Set	All subjects who received at least 1 dose of the study treatment (Exposed Set) that report unsolicited AEs/report not having unsolicited AEs

**CONFIDENTIAL**205416 [MENB REC 2ND GEN-038 (V72\_72)]  
Protocol Amendment 4 Final

For analyses of the safety endpoints, subjects will be analysed “as treated” according to the actual vaccination a subject received. The list of protocol deviations that would result in exclusion from the PPS is available in Section 4.2.2.1 of the Statistical Analysis Plan.

**Subgroups:**

- Analyses of the primary objectives will be repeated by age group (10-17 years of age and 18-25 years of age), race, sex and US region, and subjects with and without a previous MenACWY vaccination (primed and unprimed) as relevant.
- Additional subgroup analyses may be performed to assess the impact of any COVID-19 pandemic. More details will be provided in the Statistical Analysis Plan if applicable.

**10.3. Statistical analyses****10.3.1. Subjects disposition**

Number of subjects enrolled, vaccinated subjects (at least 1 vaccination, full vaccination course) and completed will be described by group. Reason for early withdraw will be described by group. Full analysis and per-protocol analysis population set will be described by group.

**10.3.2. Demography and baseline characteristics analyses**

Descriptive statistics (mean, standard deviation (SD), median, minimum and maximum) for age, height, weight, and body mass index (BMI) at enrolment will be calculated overall and by vaccine group.

Distributions of subjects by sex, race, ethnic origin will be summarised overall and by vaccine group.

**10.3.3. Primary effectiveness and immunogenicity analyses**

Refer to [Glossary of terms](#) for definitions of test-based and responder-based vaccine effectiveness.

**10.3.3.1. Vaccine effectiveness (Test-based): rMenB+OMV NZ - 3 doses (0,2,6-months schedule)**

Analysis set: Per-protocol set (PPS) will be the primary analysis population

Statistical method: The VE is defined as  $1 - RR = (1 - \text{percentage of samples without bactericidal serum activity at 1:4 dilution in MenB group} / \text{percentage of samples without bactericidal serum activity at 1:4 dilution in the Control group}) \times 100\%$  and it will be analyzed using a generalised linear model with vaccine group, strain and centre as independent variables. Furthermore, a repeated statement will be used to estimate the variance of the RR including correlation within subject's responses. A centre effect will be tentatively included in the analysis; if the statistical model does not converge due to

**CONFIDENTIAL**205416 [MENB REC 2ND GEN-038 (V72\_72)]  
Protocol Amendment 4 Final

the factor “centre”, a model without centre effect will be fitted instead. The response variable of the model will be the Bernoulli distributed outcome without bactericidal activity at a 1:4 dilution (i.e. response is 1 if titre < 4, and 0 if titre ≥ 4), at 1 month after the last vaccination (Month 7) in the MenB group and at Month 1 for the ACWY group. Each subject will contribute with approximately 35 measures to this analysis, each of the measures corresponding to the response variable to one of the 35 strains randomly assigned to be tested with the samples available for that specific subject. For the statistical analysis it is assumed that the response to each strain is an independent measure with a unique true underlying rate and VEs are expected to vary among the strains. In order to obtain the VE measure which is a measure based on the relative risk (RR), a generalised linear model will be used with the Binary distribution and link function log in order to compute the log RR and the corresponding 97.5% CI. If this model would not converge, the Poisson distribution will be used instead. The obtained values will be exponentiated to obtain the RR and the corresponding 97.5% CI. The VE will be computed as  $100\% \times (1 - RR)$ . Effectiveness of rMenB+OMV NZ will be demonstrated if the lower limit of the two-sided 97.5% CI for VE against the selected strain panel between MenB and the ACWY group is above 65%.

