**7.2.2.2.1. Study group and treatment number allocation**

The target will be to enrol a total of 3651 eligible subjects who will be randomly assigned to 6 study groups in a 5:5:3:3:3:1 ratio (912 each in MenB\_0\_2\_6 and MenB\_0\_6 groups, 548 in each ABCWY group and 183 in ACWY group).

**CONFIDENTIAL**205416 [MENB REC 2ND GEN-038 (V72\_72)]  
Protocol Amendment 4 Final

Allocation of the subject to a study group/a treatment number at the investigator site will be performed using a randomisation system on internet (SBIR). The randomisation algorithm will use a minimisation procedure accounting for study, region (US and ex-US countries), previous MenACWY vaccination (primed)? (Yes and No)\*, and age category (10-17 years of age and 18-25 years of age). Minimisation factors will have equal weight in the minimisation algorithm.

To ensure adequate representation in the US in line with the post-marketing commitment (Section 3.1), a minimum of 30% of adolescents and young adults will be enrolled in the US.

After obtaining the signed and dated ICF/IAF from the subject/subject's parent/LAR and having checked the eligibility of the subject, blinded site staff will access SBIR. Upon providing the subject identification number, the subject's age category and previous MenACWY vaccination? (Yes/ No)\*, the randomisation system will determine the study group and will provide the treatment number to be used for each dose. The number of each administered treatment must be recorded in the eCRF on the Vaccine Administration screen.

When SBIR is not available, please refer to the SBIR user guide or the SPM for specific instructions.

If for any reason, after randomisation the subject fails to undergo treatment, this is an early Termination and the reason should be recorded in source document as specified in the SDA.

Note that enrolment will be frozen as soon as the target numbers (Table 7) are reached. Refer to the SPM for further details.

Note: \* Subjects with and without a previous MenACWY vaccination (primed and unprimed).

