### 10.1.1. Hypothesis testing strategy

Multiple objectives and endpoints require type I error control. Full alpha (0.05) is split equally (alpha=0.025) between rMenB+OMV NZ objectives and MenABCWY objectives. Furthermore, within rMenB+OMV NZ, as well as within MenABCWY, objectives are tested hierarchically. If the first null hypothesis is rejected, then the testing will continue with the second hypothesis at same alpha. Same for 3rd, 4th, and so forth. Whenever a null hypothesis is not rejected, then the testing will stop.

As the comparator for MenABCWY non inferiority objective for the B component will be the selected schedule of rMenB+OMV NZ as determined in this study, the objectives of rMenB+OMV NZ will be analysed first. Additionally, if all null hypotheses related to rMenB+OMV NZ objectives will be rejected, the alpha (alpha=0.025) will be propagated to the MenABCWY part, and hypotheses related to MenABCWY objectives will be tested at full alpha (alpha=0.05). See Figure 2 for an explanation of the hierarchical testing (top to bottom, the order indicated by the arrows).

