**10.3.3.6. Effectiveness (Responder-based): rMenB+OMV NZ - 2 doses (0,2-months schedule)**

See Section 10.3.3.2

**CONFIDENTIAL**205416 [MENB REC 2ND GEN-038 (V72\_72)]  
Protocol Amendment 4 Final**10.3.3.7. Lot-to-lot consistency: MenABCWY - ACWY component**

Analysis set: The analysis of lot-to-lot consistency will be based on the PPS.

Statistical method: For each of the three ABCWY lots (Lots 1, 2 and 3 of the MenACWY component of the ABCWY vaccine), GMTs and 97.5% CIs will be calculated by exponentiating (base 10) the least squares means and the lower and upper limits of the 97.5% CIs of the log transformed titres (base10) obtained from a two-way Analysis of Variance (ANOVA) with factors for vaccine lot and study centre. Additionally, lot-to-lot GMT ratios will be computed for each pair of ABCWY lots. Ninety-seven point five percent (97.5%) CIs for the ratios of GMTs will be constructed by exponentiating the difference of the least square means of the log transformed titres and the lower and upper limits of the 97.5% CIs on the difference obtained from the ANOVA model above.

Lot-to-lot consistency criterion: The three ABCWY lots will be considered equivalent if for each of the 4 serogroups A, C, W and Y and each pair of vaccine lots, the two-sided 97.5% CI on the ratio of GMTs at 1 month after the last vaccination will be contained within the interval [0.5, 2.0]

**10.3.3.8. Immunological non-inferiority: MenABCWY vs. MenACWY in subjects without a previous MenACWY vaccination (unprimed)**

Analysis set: PPS will be the primary analysis population.

Statistical method: The percentage of subjects with 4-fold rise in hSBA titres against MenACWY indicator strains A, C, W and Y and the corresponding exact two-sided 97.5% CIs based on Clopper-Pearson method will be calculated for the ABCWY (pooled lots) group and the ACWY group [Clopper, 1934]. The 97.5% CIs for the difference in percentages between ABCWY (pooled lots) and ACWY group will be constructed using the method of Miettinen and Nurminen [Miettinen, 1985].

Non-Inferiority criterion: Non-inferiority of MenABCWY vaccine for the proportion of subjects with 4-fold rise will be demonstrated if the lower limit of the two-sided 97.5% CI for the difference in percentage of subjects with 4-fold rise between the 2 groups (ABCWY (pooled) lots –ACWY) is above -10%.

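### The test-based VE model and the lot-to-lot ANOVA omit age category and previous MenACWY vaccination, and the lot ANOVA also omits the measured Day 1 titre, so their intervals tend to be wider than needed

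*Protocol*

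**What the plan says.** Allocation (Protocol 7.2.2.2.1): "The randomisation algorithm will use a minimisation procedure accounting for study, region (US and ex-US countries), previous MenACWY vaccination (primed" status, yes or no) and "age category (10-17 years of age and 18-25 years of age"), all with equal weight.

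Test-based VE (10.3.3.1): "it will be analyzed using a generalised linear model with vaccine group, strain and centre as independent variables". Centre is provisional: "A centre effect will be tentatively included in the analysis", and it is removed if it prevents convergence. Clustering is handled: "a repeated statement will be used to estimate the variance of the RR including correlation within subject's responses". The MenABCWY test-based VE analysis (10.3.3.9) refers back to the same model.

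Lot-to-lot consistency (10.3.3.7): GMTs and their ratios come from a "two-way Analysis of Variance (ANOVA) with factors for vaccine lot and study centre". The GMT comparisons in 10.3.4.4 use an ANOVA with centre.

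Related facts:
- Table 13 lists Day 1 hSBA for A, C, W and Y at priority rank 1 and for the four B indicator strains at rank 2. It lists no enc-hSBA at Visit 1.
- The footnote to Table 6 restricts only the non-inferiority comparison with MenACWY to unprimed subjects. Primed subjects therefore enter the lot analysis, and 10.1.2.8 allows for up to 30% of them.
- Age and priming otherwise appear only as subgroup repeats (10.2).

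**The concern.** Factors used to balance allocation are normally carried into the analysis. If they predict outcome and are left out, the balance they create is not credited in the standard error, and the interval tends to be conservative. Previous MenACWY vaccination should predict A/C/W/Y titre, and the Day 1 titre is a further candidate predictor. In the lot ANOVA the variation due to both stays in the residual, except for any part that centre absorbs.

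Lot consistency is where this matters most. It is the first MenABCWY hypothesis in the order listed in 10.1.1.7 to 10.1.1.11. Section 10.1.1 stops testing at the first hypothesis that is not rejected, so a miss on any of 12 comparisons would end the MenABCWY sequence. For VE there is a smaller structural point: centre lies within region, so it carries region implicitly. If centre is dropped, no minimisation factor remains in the model.

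**Working it through.** **Lot consistency: inputs.** From 10.1.2.7 and Table 20: 411 evaluable per lot, true ratio 1.2, limits 0.5 and 2.0, 12 independent comparisons. Planning SDs (80% upper limits) are A 0.6167, C 0.5508, W 0.4043, Y 0.6846. Observed SDs are 0.5652, 0.5048, 0.3705, 0.6274. The two-sided 97.5% CI follows from "Full alpha (0.05) is split equally (alpha=0.025) between rMenB+OMV NZ objectives and MenABCWY objectives", so z = 2.2414.

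**Formula.** SE = SD × √(2/411). Power per comparison = Φ[(log10 2 − log10 1.2)/SE − z] + Φ[(log10 2 + log10 1.2)/SE − z] − 1. Joint power is the product over four serogroups, each cubed for three lot pairs.

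**Reproducing the plan.** For Y, SE = 0.6846 × √(2/411) = 0.0478. The near limit gives 0.2218/0.0478 − 2.2414 = 2.40, and power is 99.2% (stated 99.0%). A gives 99.8% (stated 99.7%); C and W exceed 99.9%, as stated. Joint power is 97.0% against the stated 96.1%. The product of the stated rounded figures for A and Y, 0.997³ × 0.990³, is 96.2%. The agreement is close enough to proceed.

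**With covariates.** Replace SD by SD × √(1 − R²), where R² is the share of log10 titre variance explained. The protocol gives no value, so 0.1-0.3 is an assumption.

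| R² | SE reduction | Joint power, planning SDs |
|---|---|---|
| 0 | – | 97.0% |
| 0.1 | 5% | 98.6% |
| 0.2 | 11% | 99.5% |
| 0.3 | 16% | 99.8% |

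At the observed SDs with no covariates, joint power is already 99.2%. If all rMenB+OMV NZ objectives are met and the lot test moves to 95% CIs, it is 98.7% at the planning SDs with no covariates.

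**Test-based VE: inputs.** From 10.1.2.1: 684 versus 137 evaluable, 35 strains each, 22% versus 75% of tests without activity, RR limit 0.35.

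**Formula.** Var(log RR) = DEFF × [0.78/(0.22 × 684 × 35) + 0.25/(0.75 × 137 × 35)] = DEFF × 0.0002176. Power = Φ[(ln 0.35 − ln(0.22/0.75))/SE − z].

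**Reproducing the plan.** With DEFF = 1, the 75%/25% row of Table 18 gives 84.0% (30 strains) and 89.5% (35 strains), against the stated 84.4% and 89.3%.

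**With covariates.** DEFF = 1 + 34 × ICC × (1 − R²). ICC and R² are assumptions.

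| ICC | R² | SE without → with | Power without → with |
|---|---|---|---|
| 0.1 | 5% | 0.0309 → 0.0303 | 99.97% → 99.98% |
| 0.2 | 5% | 0.0412 → 0.0403 | 98.0% → 98.4% |
| 0.3 | 10% | 0.0494 → 0.0471 | 90.9% → 93.5% |

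The first row is a fall of about 2% in SE. A visible power gain needs a much larger ICC.

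**The case against.** The strongest reply is that nothing is wrong here, only inefficient. Omitting balanced prognostic factors tends to widen intervals; it does not raise type I error. VE power is stated as above 99.9% at the planning rates. The lot calculation starts from deliberately pessimistic SDs, and centre may already absorb some of the variance credited to the covariates. All of this stands, and it limits the point to an improvement in efficiency.

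Some stronger readings are tempting but are not supported:

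- **Baseline titre is missing from the VE model.** No enc-hSBA is run at Visit 1, so there is no baseline value of that outcome to adjust for.
- **Centre is the wrong factor and should be replaced.** The allocation text lists study before region; within a single trial that may be a truncation of study centre. Centre also carries region, and it may carry country and site differences that a two-level region term would lose. Many centres might lack an ACWY subject, but the protocol gives no number of centres, so that cannot be sized from the documents.
- **The data choose the primary model.** The protocol pre-specifies the removal of centre, and the trigger is non-convergence, not the VE result.
- **All primary analyses are affected.** The responder analyses are single-group exact intervals. The two non-inferiority analyses use Miettinen-Nurminen without covariates, and priming is constant in the comparison with MenACWY. These lie outside the point.

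The subgroup repeats by age and priming do not answer the point, because they do not narrow the primary interval.

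**Conclusion.** The point holds for two analyses. The test-based VE model and the lot-to-lot ANOVA omit age category and previous MenACWY vaccination, although both are recorded at randomisation and used to balance it. The lot ANOVA also omits a Day 1 titre measured at first priority. The protocol itself fixes these models, so this is not a detail left to the SAP.

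The main benefit is in the lot analysis: roughly 1.6 to 2.8 percentage points of joint power at the planning SDs, and less than one point at the observed SDs. This rests on the assumed R² of 10-30%, on its being additional to what centre explains, and on the plan's assumption of independent comparisons. For VE the gain is small unless within-subject correlation is sizeable. The sounder reason to act there is that the model would still contain the minimisation factors if centre is dropped. It would be wrong to infer that either test is invalid or biased.

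**What to change.** Before unblinding, amend the model wording in the protocol and align the SAP:

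- **10.3.3.7, and the hSBA GMT comparisons in 10.3.4.4:** keep centre and lot or group. Add baseline log10 titre for the same serogroup or strain, previous MenACWY vaccination and age category (ANCOVA).
- **10.3.3.1, and 10.3.3.9, which refers to it:** add age category and previous MenACWY vaccination to group, strain and centre. If centre is dropped for non-convergence, keep both and add region.
- **7.2.2.2.1:** clarify what study means in the list of minimisation factors.

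The cost is wording and programming. All variables are already collected, and age and priming are two-level terms. The ANCOVA needs a stated rule for Day 1 titres that are missing or below the quantitation limit. With a log link, the adjusted VE targets the same RR as the unadjusted one if the RR is common across age and priming levels; the planned subgroup repeats will help to show whether that is reasonable.
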